# Design

Multicentre pragmatic randomised, multi-factorial, open-label trial with an embedded randomised double-blind, placebo-controlled, parallel group trial with internal pilot.

There will be up to three randomisations for each participant for the three trials i.e Diagnostic, Fluids or GM-CSF trial. In the first two, eligible patients with sepsis will be randomised on inclusion to

- (i) either PCR and procalcitonin guided antibiotic therapy or standard care in a 1:1 allocation ratio
- (ii) either a conservative fluid strategy with de-resuscitation or standard care in a 1:1 allocation ratio.

In the eligible subset of more severely ill patients (~35% of the total trial population) the third randomisation will allocate patients to the addition of GM-CSF or placebo in a 1:1 ratio.

Enrolment and allocation to treatment arms will be performed using an online system to ensure concealment. Treatment allocation will be by minimisation and will include a 20% random element.(41) The minimisation stratification variables will be:

- Diagnostic trial: Centre, vasopressor use (Y/N), source of infection (community vs hospital acquired)
- Fluid trial: Centre, respiratory support (Y/N), vasopressor use (Y/N)
- GM-CSF trial: Centre, allocation to Diagnostic and Fluid trials, source of infection (community vs hospital acquired)

We include an internal pilot study to assess adequate recruitment rates to each of the trials. The internal pilot will run for the initial 8 months of recruitment (~350 patients) and run seamlessly into the main trial, if the success criteria are met (see data analysis section for details). The internal pilot outcome and recruitment will be examined at 4 and 8 months. The 4-month look will allow for corrective action only.

The TSC will monitor recruitment and completion of follow-up to the primary outcome (day 90).

The TSC will also informally monitor measures of adherence:

- The median time to the PCR results being available in the intervention arm of the diagnostic trial
- The average separation in total fluid balance at day 3 in the fluid trial
- Adherence to IMP administration in the GM-CSF trial

Sponsor: Imperial College London

Version 1.1 22-Aug-2023

[figure not shown]
# **Table 1: Summary of treatment groups**

Trials	Number of participants	Intervention 1	Intervention 2
Diagnostic trial	3758	PCR and procalcitonin guided antibiotic therapy	Standard care
Fluid trial	3758	Conservative fluid therapy & de-resuscitation	Standard care
GM-CSF trial	1300	GM-CSF	Placebo

Sponsor: Imperial College London

Version 1.1 22-Aug-2023

Figure 1: Study flow chart

Sponsor: Imperial College London

Version 1.1 22-Aug-2023

#### 5. PARTICIPANT ENTRY

# Study setting and population

The target population is adult patients admitted to UK ICUs due to suspected sepsis.

#### Inclusion criteria

- Adults (≥16 years of age) admitted to ICU due to suspected sepsis and expected to stay for at least two calendar days (i.e. expected to still to be in ICU the day after tomorrow).
- Receiving intravenous antibiotics for suspected sepsis
- According to local clinical judgement, patient has received adequate initial early fluid resuscitation

**Suspected sepsis definition:** Within the context of this study, 'suspected sepsis' is defined as 'acute organ dysfunction associated with suspected infection'.(23) We do not mandate a specific definition for 'acute organ dysfunction' and will use local clinical decision. Patient characteristics underpinning local clinical decisions will be captured as part of the Case Report Form (CRF) which will include the Sequential Organ Failure Assessment (SOFA) score.

### Additional inclusion criteria for GM-CSF trial only (can be after initial trial entry):

- Intubated and mechanically ventilated and expected to continue for another 24 hours
- Or requiring two organ support (i.e. vasopressors or renal replacement therapy)
- An absolute lymphocyte count < 1.2 x10^9/L on two consecutive calendar days at least 12 hours apart, with no values >1.2 x10^9/L in between.

#### **Exclusion criteria**

- More than 24 hours since ICU admission (this does NOT apply for intervention 3, GM-CSF).
   Note: As early intervention in sepsis is important, the aim should be to enrol eligible patients as soon after ICU admission as is practically possible.
- Previously admitted to ICU due to sepsis on this hospital admission
- Not expected to survive 90 days, due to pre-existing chronic (end-stage) disease
- Not expected to survive initial resuscitation (24 hours)
- Neutropaenia (<0.5 neutrophils x10^9/L) due to chemotherapy/malignancy (but not due to sepsis)
- A source of infection that will require a prolonged course of antibiotics, for greater than 21 days (e.g. infective endocarditis, osteomyelitis, hepatic or cerebral abscess, tuberculosis)
- Diabetic ketoacidosis (DKA) or hyperglycaemic hyperosmolar state (HHS)
- Within 21 days of a spontaneous subarachnoid haemorrhage
- Diabetes Insipidus
- Weight <40Kg

#### Additional exclusion criteria for GM-CSF trial only:

- More than 120 hours (5 days) since ICU admission
- Already receiving G-CSF or GM-CSF
- A total white blood cell count (WBC) >50 x10^9/L
- Allergy, anaphylaxis or previous adverse reaction to GM-CSF or yeast-derived products

Sponsor: Imperial College London

Version 1.1 22-Aug-2023

- Known to be pregnant or breastfeeding
- Known recent (required treatment within the last 5 years) haematological malignancy
- Solid organ or bone marrow transplantation Patient weight >125kg

#### 6. PROCEDURES AND MEASUREMENTS

# Identification and recruitment of participants

Patients will be identified by local clinical and clinical research staff employed in the recruiting hospitals.

#### Screening and pre-randomisation evaluations

No additional tests or data are required for screening to assess eligibility for the trial. The screening will be conducted by local clinical and clinical research staff employed in the recruiting hospitals, using the routinely clinically collected data.

#### Randomisation and Blinding

Participants will be allocated to interventions using minimisation with a 20% random element.(41) Allocation to the first two interventions (diagnostic and fluid trials) will occur concurrently. Participants who are sicker on admission or deteriorate will be eligible to be allocated to the third intervention (GM-CSF trial). The following variables will be used for minimisation:

- Diagnostic trial: centre, vasopressor use (Y/N), source of infection (community vs hospital acquired)
- Fluid trial: centre, respiratory support (Y/N), vasopressor use (Y/N)
- GM-CSF trial: Centre, allocation in Diagnostic and Fluid trials, source of infection (community vs hospital acquired)

Concealment will be achieved through use of an online system; however, the diagnostic and fluid trials are open-label whereby participants, the clinical team and study team will not be masked to the interventions. No aggregated data by arm will be available to the study team throughout the trial.

The GM-CSF trial will be double-blind whereby the participants, clinical team, and study team will be masked to treatment allocation. This will be achieved by providing GM-CSF and matching placebo (supplied and imported from the USA by Partner Therapeutics) in similar vials and then masked by over-labelling the vials and packaging in individual numbered patient packs.

### Code-breaking/ Unblinding

Each participant will be assigned a unique trial ID which is linked to the treatment allocation. The treatment code must not be broken except in medical emergencies when the appropriate management of the participant necessitates knowledge of the treatment, or in the event that expedited reporting to the Research Ethics Committee (REC) and MHRA of a Suspected Unexpected Serious Adverse Reaction (SUSAR) is required.

The trial EDC system (on OpenClinica) will include an automated unblinding facility, in case unblinding is required. In the event that emergency unblinding of an individual participant is required,

Sponsor: Imperial College London

Version 1.1 22-Aug-2023

authorised staff (as documented on the delegation log) will follow trial procedures to unblind the participant in question and proceed with expedited reporting if required.

Investigators are encouraged to discuss the need for emergency unblinding with the Sponsor / Chief Investigator (or designee) / ICTU, if the circumstances permit such a discussion. If discussion prior to emergency unblinding cannot take place, the coordination centre (ICTU) should be informed afterwards.

Sponsor: Imperial College London

Version 1.1 22-Aug-2023

# **Visit Schedule**

Visit	Day 0 (pre randomisation)	Day 1 (post- randomisation)	Day 2	Day 3-5	Day 6-12	Day 12-28	Day 90	Day 180	Day 365
Screening	X	randomicationy							
Informed Consent (Patient consent/ PerLR/ ProLR / Retrospective Patient Information & consent)		Patient / PerLR / ProLR will be obtained initially. Retrospective patient consent will be obtained when the patient has recovered capacity to consent.							
Inclusion / Exclusion criteria	Х								
Randomisation to diagnostic & fluid trials	Х								
Randomisation to GM-CSF trial	_	Anytime up to 5 days (120 hours) after ICU admission once meets additional inclusion / exclusion criteria							
PCR & PCT test if in relevant arm of diagnostic trial.		X PCT only on Day 2							
Conservative fluid management & de-resuscitation if in relevant arm of fluid trial		Х	Х	X					
Study drug (GM-CSF / placebo) administration		For 8 d	ı lays after raı	ndomisatio	on				

Sponsor: Imperial College London

Version 1.1 22-Aug-2023

Research blood samples for all patients		X	Additional samples if in GM-CSF trial						
Data Collection / Follow up									
Baseline data	Х	Х							
Daily collection of clinical data up to Day 28 while in ICU		Х	Х	х	Х	Х			
Final hospital data collection on discharge from hospital (up to Day 90 max)							х		
Day-90 vital status							Х		
EQ-5D-5L & MOCA-Blind. (Final contact with patient)								Х	
1 year vital status (through data linkage only)									Х
Final Visit									Х

Sponsor: Imperial College London

Version 1.1 22-Aug-2023

#### **Treatment**

Treatments within the trial will only be provided while the patients are in the ICU and will be provided by local clinical staff.

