# **Secondary Endpoints**

- Duration of mechanical ventilation, vasopressor use, renal replacement therapy during index hospital admission up to 90 days
- Length of stay in ICU and hospital up to 90 days
- Antibiotic use (defined daily doses per 1000 occupied bed days and antibiotic-free days) during index hospital admission up to 28 days
- Infection relapse / recurrence or secondary infection requiring further antibiotic treatment during index hospital admission up to 28 days
- Adverse events and adverse drug reactions (including antibiotic related adverse events) during index hospital admission up to 28 days
- Health-related Quality of Life (EQ-5D-5L) and cognitive function (MoCA-Blind) at 6 months
- 1-year mortality
- Incremental costs per Quality-Adjusted Life Year (QALY), and Incremental Net monetary Benefits (INB)

Sponsor: Imperial College London

Version 1.1 22-Aug-2023

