#### 5.6.3 GM-CSF

Intervention / control – GM-CSF (sargramostim) / placebo

In the subset of patients requiring mechanical ventilation, or with two or more organ failures and with persistent lymphopaenia (defined as an absolute lymphocyte count <1.2 x10^9/L on two consecutive calendar days at least 12 hours apart, with no values >1.2 x10^9/L in between) subcutaneous GM-CSF (sargramostim) or a matching placebo will be given.

The dose will be 500µg (two vials) for patients ≥50kg, and 250µg (one vial) for patients <50kg, once a day for 8 days in the ICU.

If the patient is discharged from the ICU before the 8th day then the study drug should be given on the ward until 8 doses in total have been, if logistics allow. It will not be a protocol deviation if this is not possible. If the patient is discharged hospital before the 8th day then the study drug will stop.

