#### 7. TREATMENTS IN GM-CSF TRIAL

#### Treatment arms

Eligible patients will be randomised to one of two treatment arms

GM-CSF (sargramostim) - 500µg (two vials) for patients ≥50kg, and 250µg (one vial) for patients <50kg, given subcutaneously once a day for 8 days.

or

Matching placebo - two vials for patients ≥50kg, and one vial for patients <50kg, given subcutaneously once a day for 8 days.

Sponsor: Imperial College London

Version 1.1 22-Aug-2023

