# **Adverse Event recording**

As this is a trial is conducted in critically ill patients with life-threatening sepsis then adverse events are expected to occur regularly in most, if not all, patients. Therefore, unless an adverse event is assessed to meet Serious Adverse Event criteria, these adverse events will not be reported in the case report form and simply noted in the patient's local medical record.

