# Reporting of SAEs

As the primary outcome of the trial includes mortality, then death does not require reporting as an SAE unless, in the opinion of the local PI, the death was attributable to a study intervention / IMP or the trial protocol.

Similarly, the secondary outcomes have been selected to capture the most commonly occurring safety events in critically ill patients (e.g. organ failure and support, and new infection, including Confidential 36

Sponsor: Imperial College London

Version 1.1 22-Aug-2023

Clostridium Difficile infection). Therefore, any events that are captured as an outcome in the eCRF do not require reporting as an SAE unless in the opinion of the local PI the event was attributable to a study intervention / IMP or the trial protocol.

Rapid reporting of all SAEs i.e. within 24 hours, occurring during the patient's ICU stay up to a maximum of 28 days must be performed as detailed in the study-specific safety reporting instructions.

Active monitoring of participants after discharge from ICU or after 28 days is not required, but if the investigator becomes aware of safety information that appears to be drug or trial related, involving a participant who participated in the study, even after an individual participant has completed the study, this should be reported to the Sponsor.

All SAEs will be reviewed by the Chief Investigator or a designated medically qualified representative to confirm expectedness and causality.

Reporting of SAEs and review by the CI will be via the trial data collection system (CRF/eCRF)

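### The Treatment section confines all trial treatment to the ICU, but GM-CSF/placebo continues on the ward, where required SAE reporting has already ended

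*Protocol*

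**What the plan says.** **Where treatment is given.** Section 6, Treatment, opens with one rule for the diagnostic, fluid and GM-CSF trials together: "Treatments within the trial will only be provided while the patients are in the ICU and will be provided by local clinical staff". No exception follows.

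**GM-CSF/placebo.** Subsection 5.6.3 first describes 8 daily doses in the ICU. It then deals with a patient who leaves the ICU before the 8th day: "day then the study drug should be given on the ward until 8 doses in total have been, if logistics allow". If this cannot be done, it is not a protocol deviation. The location-based end of dosing is hospital discharge: if that comes before the 8th day, "day then the study drug will stop". Section 7, Treatment arms, has study drug "given subcutaneously once a day for 8 days" with no ICU limit. The Visit Schedule likewise counts 8 days from randomisation.

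**Safety reporting.** Section 8, Reporting of SAEs, says that rapid reporting of SAEs "occurring during the patient's ICU stay up to a maximum of 28 days must be performed". It adds: "Active monitoring of participants after discharge from ICU or after 28 days is not required". After that point, the investigator should still tell the sponsor of safety information that comes to their attention and appears related to the drug or the trial. Section 8, Adverse Event recording, says of events that do not meet SAE criteria that "these adverse events will not be reported in the case report form".

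**The endpoint.** The corresponding entry under Secondary Endpoints (section 3) is: "Adverse events and adverse drug reactions (including antibiotic related adverse events) during index hospital admission up to 28 days".

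**The concern.** The general rule and the GM-CSF rule cannot both hold for a patient who leaves the ICU part-way through the course. A site that follows the general sentence stops study drug at ICU discharge, and a site that follows 5.6.3 continues it. Exposure could then differ between sites because of wording. That would feed into the informal adherence measures (proportions receiving at least 50% and 75% of study drug) and into the supplementary estimands defined by number of doses received.

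The safety side matters more. Sargramostim is not licensed in the UK and is given blinded here, and section 7 requires permanent discontinuation for a white cell count above 50 x10^9/L or a serious allergic reaction. Yet the ward days on which it may still be given lie outside the period of mandatory SAE reporting. A blinded site may regard a single event as unrelated and have no duty to report it. It would then not reach central causality review, and would be missing from the between-arm comparison that could reveal an imbalance.

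**Working it through.** The protocol gives no figure to reproduce. The check compares the texts and adds a small arithmetic bound.

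**1. Do the rules conflict?**

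| Place in the protocol | When trial treatment ends |
|---|---|
| Treatment, opening sentence | ICU discharge, all trials, no exception |
| Fluid trial | Day 5 or ICU discharge, whichever is first |
| 5.6.3 GM-CSF | 8 doses, on the ward if practicable; otherwise hospital discharge |
| Section 7, Treatment arms | 8 daily doses, no location limit |
| Visit Schedule | 8 days after randomisation |

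The opening sentence agrees with the fluid trial and fails for GM-CSF. Subsection 5.6.3 is the specific rule, and the last two rows support it. The error is therefore in the general sentence.

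**2. Doses at stake.** Let k be the number of doses given before ICU discharge. Under a literal ICU-only rule the loss is

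doses lost = 8 - k.

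For k = 7 this is 1, and for k = 1 it is 7. Against the adherence thresholds, taking 8 doses as the full course: 50% is 0.50 x 8 = 4 doses and 75% is 0.75 x 8 = 6 doses. Stopping at ICU discharge leaves a participant below the 50% mark if k is 3 or fewer, and below the 75% mark if k is 5 or fewer, even where ward dosing could have completed the course.

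**3. Ward days outside required SAE reporting.** With one dose a day and no gaps, the number of ward dosing days is also 8 - k, so 1 to 7.

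**4. Would reporting to the last dose stay within 28 days?** The latest GM-CSF randomisation is 120 hours, or day 5, after ICU admission (additional GM-CSF exclusion criteria). Dose 8 falls 7 days after dose 1.

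- Dose 1 on the day of randomisation: 5 + 7 = day 12, leaving 28 - 12 = 16 days.
- Dose 1 the next day (assumption): 6 + 7 = day 13, leaving 28 - 13 = 15 days.

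These days are counted from ICU admission; any later starting point gives smaller numbers. The existing maximum therefore need not change, even if some missed doses are made up.

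**5. What escapes reporting?** An event on a ward dosing day is outside all required capture when three conditions hold together: it is serious, the site does not think it drug- or trial-related, and it is not already recorded as an eCRF outcome. Because only events meeting SAE criteria go into the case report form as adverse events, such an event could also be missing from the adverse-event endpoint, whose window runs over the index hospital admission to day 28.

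**The case against.** The strongest reply is that this is a general rule followed by a specific exception in the same section. A site cannot dose GM-CSF from the opening sentence, which gives no dose or schedule, so it must read 5.6.3. There the ICU is the default location and the ward a conditional extension. A shortened course is tolerated in any case. This stands as a reason for low severity. It does not reconcile the texts: the opening sentence allows no exception, and the ICU phrase in 5.6.3 is qualified by that subsection's own next paragraph. The tolerance for shorter courses rests on logistics, not on a site believing that ward dosing is barred.

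On safety, the reply is that an SAE window and a dosing location are not strictly contradictory. Reduced reporting is a reasoned choice in a population where adverse events are near universal. Common serious events (death, organ support, new infection) are captured as outcomes, and hospital data are collected again at discharge. Apparently related events must still go to the sponsor, and the separate safety reporting instructions may say more. These points narrow the gap considerably. They do not close it, because the residual duty depends on the investigator happening to learn of the event and thinking it related.

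It is also fair to say that the mismatch between the adverse-event endpoint window and the ICU-based SAE window exists in all three trials, with or without ward dosing. That wider mismatch is a separate matter, which the fix below does not resolve.

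**Conclusion.** The concern holds, as a minor correction. The opening sentence of the Treatment section is wrong as written for GM-CSF/placebo, and mandatory SAE reporting stops at ICU discharge although blinded dosing may continue.

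The size is 1 to 7 doses and 1 to 7 ward dosing days per affected participant. This is an arithmetic bound under daily dosing without gaps, not an estimate. The upper end is unlikely, because entry to the GM-CSF trial requires ventilation or multiple organ support. The number affected cannot be derived, since the protocol gives no ICU-discharge rate for this subset. The primary treatment-policy analysis and the sample size are unaffected.

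**What to change.** 1. **Section 6, Treatment:** add to the opening sentence an exception for GM-CSF/placebo, which continues on the ward after ICU discharge as described in the GM-CSF subsection.
2. **Section 8, Reporting of SAEs:** require SAE reporting for GM-CSF trial participants until the last dose of study drug when that dose is given on the ward, within the 28-day maximum. Give the sentence that waives active monitoring after ICU discharge the same exception.

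The ward-dosing rule in 5.6.3 can stay as it is. The cost is one clause, plus one sentence with its exception. Sites take on at most 7 extra days of SAE reporting for a participant dosed on consecutive days who finishes on the ward. Design, analysis and sample size do not change.

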# Diagnostic trial

Intervention – antibiotic optimisation using PCR-based pathogen testing and procalcitonin

A blood sample will be taken after randomisation for rapid PCR-based pathogen testing, to be sent to the designated molecular diagnostic laboratory.

Procalcitonin (PCT) will be measured on the day of inclusion and the next day (18 - 36 hours later). This will be measured in the local hospital laboratory or using a point of care device. If a sample has already been sent as part of clinical care on the day of inclusion that value can be used for trial purposes; it does not have to be repeated.

In addition, all standard microbiological sampling will continue as normal.

If the **PCR result is positive**, the antibiotic regimen will be optimised based on this result. The result from the PCR result will be sent to sites from the central coordination centre. The clinical team should seek advice from their local microbiology service as appropriate to discuss optimal antibiotic choice based on local sensitivity and resistance patterns of the identified organism(s).

If the PCR result is negative AND the procalcitonin results are negative (both results <0.5 µg/L or the second procalcitonin result has dropped by >80% from the first result) and there are no other positive microbiology results or clear objective evidence for infection, then the empiric antibiotics will be stopped. As well as standard microbiology culture techniques, other sources of evidence for infection, based on usual practice will be reviewed. These include pneumococcal and Legionella antigen tests, white cells on lumbar puncture, purpuric rash or evidence of faecal soiling seen at laparotomy. If any of these objective features of infection are present antibiotics will be continued according to local guidelines.

In all other patients (including if PCR is negative and the procalcitonin is positive, i.e. ≥0.5 µg/L without an 80% drop from first to second result), antibiotic prescriptions will be reviewed daily, in consultation with microbiology teams. Sites are advised to both de-escalate antibiotic therapy and prescribe short courses of antibiotics, as clinically appropriate, as recommended by Public Health England.(42)

